Study design	
After enrollment, the participants will receive a combined treatment regimen of Sintilimab, Ramucirumab and chemotherapy. The chemotherapy regimen will include one of the following two combination therapies: SOX regimen (oxaliplatin and S-1) or XELOX regimen (oxaliplatin and capecitabine). A maximum of 6 cycles of combination treatment will be administered, with each cycle lasting 21 days. After completing the 6 cycles of combined treatment regimen, the participants will receive Sintilimab and oral chemotherapy agents (Capecitabine or S-1) with or without Ramucirumab until disease progression. In case of disease progression or intolerable toxic reactions occur during treatment, the investigator will determine the subsequent treatment options.
 
The specific dosages and methods for the medications mentioned above are as follows:
 
Immunotherapy:
 
Sintilimab: 200mg fixed dose, intravenous infusion on Day 1, repeated every 21 days.
 
Targeted Therapy:
 
Ramucirumab: 10mg/kg intravenous infusion on Day 1, repeated every 21 days.
 
Chemotherapy: Two combination regimens include:
 
SOX regimen: Oxaliplatin 130mg/m² intravenous infusion on Day 1 and S-1 40mg/m² orally twice daily on Days 1-14, repeated every 21

days.

XELOX regimen: Oxaliplatin 130mg/m² intravenous infusion on Day 1 and Capecitabine 1000mg/m² orally twice daily on Days 1-14, repeated every 21 days.

Imaging assessments (CT/MRI) are required before the first treatment and after every two cycles of treatment. Gastric tissue specimens will be collected from patients prior to the first treatment (paraffin sections) (5-20 slices of surgical tissue (each tissue more than 1cm²), or 20-25 slices of puncture tissue). Blood samples and stool samples will be collected before the first treatment, after every two cycles, or at the time of disease progression to analyze the corresponding samples collected at baseline, when the best overall efficacy appears, or upon disease progression (Blood samples: approximately 5ml per instance; fecal samples: middle segment stool, the size of a soybean (approximately 50 mg), collected in three tubes). The expression levels of 92 proteins in blood samples will be dynamically monitored using the Olink-96 Immune-Oncology panel. Intratumoral microbiota in baseline tumor tissue samples will be detected using 5R 16S rRNA sequencing, and gut microbiota in stool samples will be detected using 16S rRNA sequencing.

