Efficacy Analysis: The Objective Response Rate (ORR) will be calculated as the proportion of patients in the ITT population who achieved the best overall response of complete response (CR) or partial response (PR). The Disease Control Rate (DCR) will be calculated as the proportion of patients in the ITT population who achieved the best overall response of CR, PR, or stable disease (SD). For efficacy endpoints such as overall survival (OS) and progression-free survival (PFS), the Kaplan-Meier method will be used to estimate the median times and list the median events along with their two-sided 95% confidence intervals.

Patient data and outcome parameters will be inputted into GraphPad Prism (version 9.1.2) and analyzed using the non-parametric Mann-Whitney U test (for continuous variables) to compare differences between two groups. For comparisons among more than two patient groups, the non-parametric Kruskal-Wallis test will be applied, followed by Dunn's post-hoc test with Bonferroni correction. Fisher's exact test will be used for intergroup comparisons of categorical variables.

The serum protein abundance data from patients receiving Sintilimab + Ramucirumab + chemotherapy will be analyzed using the Cox proportional hazards model and Benjamini-Hochberg

	
multiple hypothesis correction ("R," version 4.2.1). A sample will be identified as an outlier using PCA plots and median vs. interquartile range (IQR) plots. This sample will be excluded from the phase one analysis. Samples with QC warning status will also be excluded from both analyses on a per-panel basis. The results will then be adjusted for multiple testing using the Benjamini-Hochberg method. Hazard ratio (HR) will be based on 1 NPX difference. The association between baseline NPX (v1) and ΔNPX (Δv2/v3-v1) plasma protein levels and PFS will be assessed by plotting Kaplan-Meier curves and calculating log-rank p-values. Patients receiving Sintilimab + Ramucirumab + chemotherapy will be evaluated by dividing them into low or high expression "risk groups" based on the median expression values of each parameter as a threshold. For all statistical analyses, a p-value of less than 0.05 will be considered statistically significant.

Research progress	August 2024 - July 2026

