3.1. Study Design

[figure not shown]
This study is a prospective, single-arm, single-center, phase II clinical trial. A total of 39 patients with advanced gastric cancer with liver metastasis, who are receiving first-line treatment, will be enrolled from August 2024 to July 2025 at our center. Participants will receive the combination treatment of Sintilimab, Ramucirumab and chemotherapy, with the chemotherapy regimen including two options: SOX regimen and XELOX regimen. A maximum of 6 cycles of combination treatment will be administered, with each cycle lasting 21 days. After completing 6 cycles of chemotherapy, patients will continue with Sintilimab and an oral chemotherapy agents (Capecitabine or S-1) with or without Ramucirumab, until disease progression. If disease progression or intolerable toxic reactions occur during treatment, the investigator will determine the subsequent treatment plan.

Radiological assessments (CT/MRI) will be performed before the first treatment and after every two cycles of treatment. Tissue samples from gastroscopy (paraffin sections) will be collected from patients before the first treatment (5-20 slices of surgical tissue (each tissue more than 1cm²), or 20-25 slices of puncture tissue). Blood samples and stool samples will be collected before the first treatment, after every two cycles, or at the time of disease progression to analyze the corresponding samples collected at baseline, when the best overall efficacy appears, or upon disease progression (Blood samples: approximately 5ml per instance; fecal samples: middle segment stool, the size of a soybean (approximately 50 mg), collected in three tubes). The plasma protein expression levels of 92 proteins will be dynamically monitored using the Olink-96 Immune-Oncology panel. The intratumoral microorganisms in baseline tumor tissue samples will be detected by 5R 16S rRNA sequencing, while the gut microbiota in fecal samples will be analyzed using 16S rRNA sequencing. Samples

will be destroyed immediately after testing is completed.

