3.2. Technical Route and Testing Process

For patients with liver metastasis from advanced gastric cancer receiving first-line treatment, screening will be completed according to the inclusion and exclusion criteria outlined in the study protocol, followed by thorough communication and signing of the informed consent form. After enrollment, patients will participate in the clinical trial of the Sintilimab, Ramucirumab and chemotherapy regimen. During treatment, tumor tissue testing, peripheral blood microprotein expression testing, and fecal gut microbiota testing will be conducted according to the protocol, with timely follow-ups. Tissue samples from gastroscopy (paraffin sections) will be collected before the first treatment for the purpose of intratumoral microorganism detection (5R 16S sequencing). Blood samples and fecal samples will be collected accordingly before the first treatment, after every two cycles, or at disease progression, and testing of blood and fecal samples collected at baseline, at the time of the best overall efficacy, or upon disease progression will be conducted. The plasma protein expression levels of 92 proteins will be dynamically monitored using the Olink-96 Immune-Oncology panel. The gut microbiota in fecal samples will be analyzed through 16S rRNA sequencing.

a. Blood Sample Microprotein Expression Level Detection Method

This study employs the Proximity Extension Assay (PEA, Olink-96 Immuno-Oncology panel) technique. It involves a set of antibodies tagged with specific nucleotide sequence probes that specifically bind to the target proteins being measured. Correct and adjacent probes bind through the complementary pairing of bases at the 5' ends over 5 base pairs, forming a double-stranded template with the aid of proximity

extension enzymes. Detection is carried out using qPCR or next-generation sequencing (NGS), with the specific nucleotide sequence signals reflecting the content of the detected proteins. Olink converts the Ct values read by qPCR into relative quantification units (Normalized Protein Expression, NPX).

b. Intratumoral Microorganism Detection Method

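### Change in protein level (v2/v3 minus v1) is tested against PFS with v2 and v3 tied to no visit and no landmark; if v3 is the progression sample, it cannot serve as a predictor of PFS

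*Combined protocol and SAP*

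**What the plan says.** The protein analysis appears only in the protocol synopsis, in the row on the statistical analysis plan. It has two parts.

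- A Cox model for protein abundance, with the hazard ratio per 1 NPX and Benjamini-Hochberg correction: "The results will then be adjusted for multiple testing using the Benjamini-Hochberg method".
- Kaplan-Meier curves and log-rank tests of baseline NPX (v1) and of the change (v2/v3 minus v1): "plasma protein levels and PFS will be assessed by plotting Kaplan-Meier curves and calculating log-rank p-values". Patients are divided into low and high groups "based on the median expression values of each parameter as a threshold".

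The row closes with "For all statistical analyses, a p-value of less than 0.05 will be considered statistically significant". Section 11 repeats that rule but leaves the protein analysis out.

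On sampling, section 3.1 states: "Blood samples and stool samples will be collected before the first treatment, after every two cycles, or at the time of disease progression". On which of these samples are assayed, section 3.2 states: "testing of blood and fecal samples collected at baseline, at the time of the best overall efficacy, or upon disease progression will be conducted". The synopsis row on study design gives the same post-baseline points, "when the best overall efficacy appears, or upon disease progression", and adds: "The expression levels of 92 proteins in blood samples will be dynamically monitored using the Olink-96 Immune-Oncology panel". Section 6 places the on-treatment assay at the scan that shows the best efficacy. It triggers the later assay on worsening or new symptoms, within one week of confirmation. Section 7 counts PFS from the start of treatment to progression or death.

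**The concern.** Only v1 has a meaning. The labels v2 and v3 occur in one sentence and nowhere else, so two analysts could follow the plan and test different samples.

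The sample's date matters because PFS starts at first treatment and the covariate is measured later. A post-baseline covariate can be related to PFS only if it is measured before the period in which events are counted. The plan has no landmark, no time-dependent covariate and no rule for patients without a v2 or v3 sample.

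If v3 is the progression sample, the date of measurement is nearly the PFS time itself. A protein that rises or falls with time on treatment, and has nothing to do with prognosis, then orders patients by their PFS. Section 3.2 seeks prognostic markers for PFS, so such a protein could be reported as one.

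**Working it through.** **1. The plan's own figures.** None is given for this analysis. The one computed figure, N = 39 for ORR (section 5.1), reproduces with a one-sided 5% test: [1.645 × √(0.43 × 0.57) + 0.842 × √(0.65 × 0.35)]² / 0.22² = 30.5, so 31; 31 / 0.8 = 38.75, so 39. It does not depend on the protein analysis.

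**2. Which samples can v2 and v3 be?**

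| Source | Post-baseline blood drawn | Post-baseline blood assayed |
|---|---|---|
| Synopsis (study design), 3.1, 3.2 | every two cycles, or at progression | best efficacy, or progression |
| Section 6 | every two cycles; at symptom worsening | best efficacy; symptom worsening |
| Synopsis (statistics) | v2, v3 | v2, v3, no visit given |

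Two labels stand against two assay points. No fixed post-baseline visit is named for assay.

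**3. Who has a progression sample?** Assumptions: exponential PFS with median 7.7 months (section 1, sintilimab plus chemotherapy, CPS ≥ 5) and follow-up uniform over 5 to 17 months (enrolment August 2024 to July 2025, follow-up to December 2025, section 13).

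- Rate λ = ln 2 / 7.7 = 0.0900 per month.
- Share with an event = 1 − (e^(−5λ) − e^(−17λ)) / (12λ) = 1 − (0.638 − 0.216) / 1.080 = 0.61.
- Events: 39 × 0.61 = 23.8.

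So about 15 of 39 would have no progression sample. Some deaths may have none either.

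**4. False-positive rates (illustration).** The documents give no data on how these proteins change. Assumptions: 39 patients, a protein unrelated to PFS, unit-SD noise, the drift shown, median split, two-sided log-rank at 5%, 20,000 simulated trials per cell. The plateau form is drift × τ × (1 − e^(−t/τ)). Entries are per cent.

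| Sample and course; drift in SD per month | 0 | 0.1 | 0.2 | 0.3 | 0.5 |
|---|---|---|---|---|---|
| Progression, plateau τ = 1.5 months | 6.2 | 6.5 | 6.3 | 7.2 | 8.9 |
| Progression, plateau τ = 3 months | 6.3 | 7.0 | 9.4 | 13.3 | 25.8 |
| Progression, linear, same slope in all patients | 6.6 | 26.5 | 65.8 | 89.2 | 99.2 |
| As above, 30% of event samples missing | 7.0 | 20.4 | 49.3 | 74.1 | 93.6 |
| Best response at week 6, 12 or 18, uniform | 5.3 | 5.6 | 6.0 | 7.3 | 9.3 |
| Fixed week-6 sample with landmark | 5.3 | 5.4 | 5.4 | 5.0 | 5.7 |

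Two sensitivities matter.

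- Slopes that differ between patients lower the linear rates. At 0.2 SD per month, about 65% falls to about 33% if the slope SD equals the mean slope, and to 19% if it is twice the mean. At 0.3, 89% falls to about 40% and 21%.
- If best response may be sampled as late as the fourth scan, its rate at 0.3 SD per month is 15% to 17% (median PFS 7.7 and 5.6 months).

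After Benjamini-Hochberg, with 23 of 92 independent proteins drifting 0.2 SD per month, the mean number of falsely significant proteins is 7.7 (progression, linear, common slope), 0.17 (τ = 3), 0.13 (τ = 1.5) and 0.07 (week-6 landmark).

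**5. What a landmark leaves.** Week 6 is 1.38 months.

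- Progressed or died by then: 39 × (1 − e^(−0.0900 × 1.38)) = 4.6 (6.1 at a median of 5.6 months, 3.6 at 10 months).
- Remaining: 39 − 4.6, about 34 patients, with 23.8 − 4.6 = 19.2 events.
- If progression is dated at scans every six weeks, almost all of these early events fall on the week-6 scan itself, and about 18 events remain.
- Detectable hazard ratio (80% power, two-sided 5%, unadjusted, median split) = exp(2 × 2.802 / √events): 3.15 at 23.9 events, 3.58 at 19.3, 3.75 at 18.

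**The case against.** **The labels may mean fixed visits.** Blood is drawn every two cycles and the protein levels are said to be followed dynamically, so v2 and v3 could be, say, the samples after cycles 2 and 4. This stands. A reader might infer that the plan certainly tests a progression sample against PFS; the documents do not say so. But no fixed visit is named for assay either, and the missing definition and missing landmark are defects on both readings.

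**The later sample need not follow the PFS event.** Section 6 triggers it on symptoms, so it may precede radiological progression or occur without it. This stands too. It rules out the absolute claim that such a sample exists only after a PFS event. Its date is still patient-specific and clusters around the event, so a plain log-rank test from treatment start is no more valid.

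**The large rates come from assumed inputs.** This is correct. Rates near 90% need unlimited linear drift with the same slope in every patient, and early plateaus give almost nothing. The rates show direction and range; they do not forecast this trial.

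**Benjamini-Hochberg is already planned.** A reader might infer that the log-rank p-values are uncorrected. The text does not establish that: the adjustment sentence comes before the log-rank sentence without saying which results it covers, and a 0.05 threshold can apply to adjusted values. The scope needs stating. In any case the correction handles multiplicity and does not repair a biased test.

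**It is exploratory.** This limits the weight of the point but does not remove it, since a search for prognostic markers is a stated aim.

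**Conclusion.** The concern holds in a conditional form. It is certain that v2 and v3 have no visit and that a post-baseline change is tested against PFS from treatment start without a landmark. It is an inference, supported by the testing text, that v3 is the progression or deterioration sample. On that reading the sample cannot serve as a predictor of PFS, and this conclusion needs no simulation.

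The size of the resulting error is not known from the documents. Under the stated assumptions it runs from 6% to 9% with an early plateau to well above 5% with sustained drift, and it shrinks when slopes vary between patients. The best-response sample carries a smaller bias of the same kind, which grows with how late it may be drawn.

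This should be corrected before post-baseline protein data are analysed, but it is not critical to the trial. The ORR endpoint, N = 39 and the baseline (v1) protein analysis are untouched.

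**What to change.** - **Define the samples.** v1 is the pre-treatment sample and v2 the sample after cycle 2. Name the best-response and the progression or deterioration samples separately. Align the testing text in the synopsis and in sections 3.1, 3.2 and 6 so that the cycle-2 sample is assayed.
- **Use a landmark.** Test v2 minus v1 against PFS counted from a landmark just after the first post-baseline scan. Exclude patients with progression or death at or before that scan; this rule is needed because early progression will mostly be dated to that scan. Report how many patients leave and why.
- **Apply it to both methods.** Use the same landmark and patients for the log-rank test and for any Cox model of the change per 1 NPX.
- **Restrict the other samples.** Report progression and deterioration samples descriptively, without a test against PFS. Test best-response samples only with a method that respects the sampling time.
- **State the multiplicity rule.** Say that Benjamini-Hochberg also covers the log-rank p-values.

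Cost: wording in the SAP and the testing text, and no extra blood draw. At most about 34 extra assays are needed, fewer where best response falls at the first scan; cycle-2 blood must be kept until assayed. About 5 of 39 patients leave the change analysis, with about 18 to 19 events remaining before dropout and quality-control exclusions. The detectable hazard ratio rises from about 3.1 to about 3.6 or 3.7. The baseline analysis stays as written.

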5.1. Sample Size Calculation

Based on a clinical study conducted by Yang et al. involving 60 patients with gastric cancer liver metastasis who received chemotherapy or immunotherapy combined with chemotherapy, the experimental group ($n = 30$) received continuous

intravenous infusion of Endu combined with the SOX regimen, while the control group (n = 30) received only the SOX regimen. The overall response rates (ORR) were 63.3% and 43.3%, respectively (PMID: 30539861). Considering that immunotherapy combined with anti-vascular treatment and chemotherapy provides a better response for gastric cancer with liver metastasis compared to chemotherapy alone, it is expected that the ORR for patients receiving this combined treatment will increase to 65%. Assuming the original ORR is 43%, under the conditions of a type I error of 0.05 and a power of 0.8, and considering a dropout rate of 20%, the study plans to enroll a total of 39 participants.

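### Protein and PFS: a continuous Cox model and a median-split log-rank test are both planned, with no rule for which counts, and only the weaker test is tied by name to PFS and to ΔNPX

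*Combined protocol and SAP*

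**What the plan says.** The protein analysis appears only in the Protocol synopsis, Statistical analysis plan row. Section 11 (Statistical Processing) repeats neither part of it.

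- **Cox model.** Serum protein abundance is analysed by Cox regression with Benjamini-Hochberg correction, and "Hazard ratio (HR) will be based on 1 NPX difference". That scale implies that the protein enters as a continuous covariate. The text does not name the outcome or mention change in NPX.
- **Median split.** For baseline NPX and ΔNPX, the association between "plasma protein levels and PFS will be assessed by plotting Kaplan-Meier curves and calculating log-rank p-values". Patients are divided "into low or high expression 'risk groups' based on the median expression values of each parameter as a threshold".
- **Significance.** The synopsis and Section 11 both apply p < 0.05 to all statistical analyses.

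Section 3.2 describes the measurement: "Olink converts the Ct values read by qPCR into relative quantification units (Normalized Protein Expression, NPX"). It also says that proteins will be related to response, disease control, adverse reactions, PFS and OS. Sections 3.1 and 3.2 say that the samples tested are those from baseline, from best response or from progression. The endpoint is exploratory and has no stated power or event count.

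**The concern.** NPX is a continuous relative unit. A median split treats patients just either side of the cut as opposites, and treats everyone within a half as alike. The cut comes from the sample, so it is not an assay or clinical threshold, and a high or low label cannot be carried to another data set. Yet the split is the only method that the plan attaches by name to PFS and to ΔNPX, and its p-values are inferential as written.

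Two things are at stake in a search through 92 proteins in at most 39 patients. If the log-rank result decides, real associations are missed more often than they need be. If either result may decide, two p-values per protein give two chances of a false positive, and the tests can disagree with no rule to settle it.

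**Working it through.** **1. The plan's own figure.** Section 5.1 says "the study plans to enroll a total of 39 participants". With response rates of 43% and 65%, one-sided 0.05 and power 0.80:

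n = [1.645·√(0.43×0.57) + 0.842·√(0.65×0.35)]² / 0.22² = 30.5, so 31; 31/0.8 = 38.75, so 39.

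The figure reproduces, but it is sized for ORR. Nothing was sized for proteins.

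**2. Information kept by a median split.** For a normal marker, the two half-sample means lie 2√(2/π) SD apart. With d events and β = ln(HR per SD), at two-sided 0.05:

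- continuous Cox power ≈ Φ(√d·β − 1.96)
- median-split log-rank power ≈ Φ(√(2d/π)·β − 1.96)

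The ratio of information is 2/π = 0.637, and 39 × 0.637 = 24.8. So 39 patients split at the median carry about as much as 25 analysed continuously. Example with d = 25 and HR 1.75 (β = 0.560): Φ(2.80 − 1.96) = 80% against Φ(2.23 − 1.96) = 61%.

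**3. Inputs for simulation.** From the documents: n = 39. Section 13 ends enrolment in July 2025 and follow-up in December 2025, which gives about 5 to 17 months of follow-up per patient. Assumed: uniform censoring over that span, exponential PFS, normal NPX known at time zero, log-linear hazard, two-sided 0.05, and the effect sizes. The assumed median PFS is 7.7 months, from the sintilimab-plus-chemotherapy phase III trial cited in Section 1. That figure is for CPS ≥ 5, and this trial has no CPS criterion.

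Expected events: λ = ln 2/7.7 = 0.0900; P(event) = 1 − (e^(−5λ) − e^(−17λ))/(12λ) = 1 − (0.638 − 0.217)/1.080 = 0.61; 39 × 0.61 ≈ 24.

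**4. Power under a log-linear effect**

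| HR per SD | Continuous Cox | Median-split log-rank | Difference (points) |
|---|---|---|---|
| 1.2 | 14% | 11% | 3 |
| 1.4 | 35% | 25% | 10 |
| 1.5 | 47% | 32% | 15 |
| 1.6 | 58% | 40% | 18 |
| 1.75 | 72% | 51% | 21 |
| 2.0 | 87% | 68% | 20 |
| 2.5 | 97% | 85% | 12 |
| 3.0 | 99.5% | 94% | 6 |

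Differences are taken before rounding. Variations:

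- All 39 patients with events, HR 1.6: 75% against 55%.
- 31 patients, HR 1.6: 48% against 33%.
- Per-test level 0.005, a stand-in for multiplicity control, HR 1.75: 37% against 20%.

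**5. Power under a step effect at the median.** The order reverses. With about 24 events, Cox against log-rank is 26% against 31% at HR 2.0, 41% against 48% at 2.5, and 54% against 62% at 3.0. If 7.7 months is instead the median of the low group, there are more events and HR 3.0 gives 63% against 72%.

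**6. False positives with no rule.** With no true association, Cox rejects in 5.5% of simulations, log-rank in 5.3%, and at least one of them in 8.4%. If all 92 proteins were null, that is 92 × 0.084 = 7.7 unadjusted false positives, against 92 × 0.055 = 5.1 for Cox alone. The Benjamini-Hochberg sentences precede the log-rank sentence, and the text does not say whether they cover it.

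**The case against.** The strongest reply is that the better analysis is already planned. A hazard ratio per 1 NPX means a continuous covariate, the multiplicity correction is attached to the Cox model, and Cox needs a time-to-event outcome. Section 3.2 names PFS and OS for the proteins. A natural reading is Cox for inference and Kaplan-Meier for display. Much of this stands. A reader might infer that the trial gives up 10 to 20 points of power, or that no continuous analysis exists. The documents support neither: adding a log-rank test takes nothing from the Cox test. But the natural reading is not written down. The outcome could be PFS, OS or both, ΔNPX appears only with the log-rank test, and p < 0.05 is declared significant for all analyses.

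Second, the power figures rest on inputs that the plan does not give, and on a log-linear hazard, which favours Cox. This also stands, as the small gap at HR 1.2 and the reversal under a step effect show. A step exactly at the sample median is, however, a special case for which the documents give no reason.

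Third, the figures do not describe ΔNPX, and this stands in full. The simulated marker is known at time zero in every patient. The later sample is tested at best response or at progression, so ΔNPX is known only during follow-up and may be measured at the PFS event itself. A continuous Cox model starting at first treatment would not cure that.

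**Conclusion.** The concern holds as a gap in specification with a measurable cost. Two tests of protein against survival are planned, none is named as decisive, and the one tied explicitly to PFS and ΔNPX discards about 36% of the information in a normally distributed marker. For baseline NPX, that test gives up 10 to 21 points of power at hazard ratios per SD of 1.4 to 2.0, conditional on the assumed event count, marker distribution and log-linear effect. Letting either test decide raises the unadjusted per-protein error rate from about 5% to about 8%. No power figure is claimed for ΔNPX.

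The importance is minor. A reader might infer that the trial's main results are at risk, but the protein work is exploratory, and the ORR, DCR, PFS, OS and safety estimates do not depend on it.

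**What to change.** Replace the log-rank and risk-group sentences with wording such as:

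*The association of baseline NPX with PFS will be tested in a Cox model with NPX as a continuous covariate (HR per 1 NPX). The Benjamini-Hochberg-adjusted p-value from this model is the only one used to declare an association. Kaplan-Meier curves by median split are illustrative and carry no p-values. Change in NPX will also be analysed as a continuous covariate, using only a sample taken before progression, with PFS counted from a fixed landmark or with ΔNPX as a time-dependent covariate.*

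State the same rule in Section 11, which is silent on the proteins.

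The cost for baseline NPX is wording only: the Cox model, the correction and the scale are already planned, and the figures are kept. The small downside is reliance on log-linearity, to be checked with residual plots for the proteins reported. For ΔNPX, a landmark drops patients who progress before it. It may also require testing a fixed-visit sample: these are collected after every two cycles, but under Sections 3.1 and 3.2 they are tested only if they fall at best response or progression.

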This study utilizes the 5R 16S rRNA gene sequencing technology, which involves multiplex PCR amplification and sequencing of five regions on the 16S rRNA gene. This effectively reduces the severe interference from host DNA in the amplification of bacterial 16S rDNA from tissue samples. After quality control, OTU clustering, and species annotation of the sequencing data, a dedicated process for filtering contaminating bacteria is employed. Bioinformatics tools are then used to calculate diversity indices and perform statistical analysis to elucidate the characteristics and functions of the microbiome within the tumor tissue.

c. Fecal Sample Gut Microbiota Detection Method

This study adopts the 16S rRNA gene sequencing technology. Genomic DNA is extracted from fecal samples, and specific primers are used for PCR amplification of the 16S region, followed by high-throughput sequencing analysis. After quality control, OTU clustering, and species annotation of the sequencing data, bioinformatics tools are utilized to calculate diversity indices and statistical analysis to reveal the composition and diversity of bacterial communities in the samples.

The study aims to identify gut microbiota or proteins related to treatment efficacy and safety, exploring the relationship between these specific microbial communities or proteins and objective response rate (ORR), disease control rate (DCR), and adverse reactions. It seeks to identify potential populations that may benefit from treatment, providing evidence for personalized precision therapy for future patients with advanced gastric cancer and liver metastasis. Additionally, the study will analyze the correlation of microbiota or proteins with patients' progression-free survival (PFS) and overall survival (OS), seeking potential prognostic biomarkers.

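### Benjamini-Hochberg is stated for the protein Cox models but not for the log-rank tests of the same proteins or across taxa, and a change score from a progression-timed sample should not be tested against PFS

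*Combined protocol and SAP*

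**What the plan says.** **Proteins.** The synopsis (Study design) states: "The expression levels of 92 proteins in blood samples will be dynamically monitored using the Olink-96 Immune-Oncology panel". Its statistical analysis plan fits Cox models per 1 NPX difference and says "The results will then be adjusted for multiple testing using the Benjamini-Hochberg method". A separate analysis follows. The association of "baseline NPX (v1) and ΔNPX (Δv2/v3-v1") with PFS "will be assessed by plotting Kaplan-Meier curves and calculating log-rank p-values", with patients divided into low and high groups "based on the median expression values of each parameter as a threshold". No adjustment is given in or after that text, and the paragraph ends with "For all statistical analyses, a p-value of less than 0.05 will be considered statistically significant". Section 11 repeats the 0.05 rule and mentions neither BH nor the protein analysis.

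**Microbiota.** Section 3.2 says "The study aims to identify gut microbiota or proteins related to treatment efficacy and safety" and names five outcomes: ORR, DCR, adverse reactions, PFS and OS. The only other correction in the plan is Bonferroni after Dunn's test, which covers pairs of groups within one variable.

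**Timing.** According to the synopsis and sections 3.1, 3.2 and 6, blood and stool are collected every two cycles, but the samples analysed are those at baseline, at best overall efficacy and at progression. PFS runs from the start of treatment (synopsis and section 7). No landmark or time-dependent handling is described, and v2 and v3 are never defined.

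**The concern.** The same proteins are related to the same endpoint by two routes. Only the Cox route has a stated multiplicity control, so a protein that fails BH there could still be called significant from its median-split log-rank p-value. The plan has no sentence that prevents this.

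The change scores raise a second problem. A progression sample exists only for patients who progressed, and it is taken later in those who progressed later. If a protein moves steadily with time on treatment, its change from baseline partly measures PFS itself.

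What is at stake is the credibility of the biomarker list. Section 3.2 wants it to point to potential populations that may benefit and to support personalised therapy, from 39 patients.

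**Working it through.** **Inputs**
- From the documents: 92 proteins; threshold 0.05; median split, so no cut-point search adds error; 39 patients (section 5.1).
- Measures per protein: 1 for baseline only, 2 if there is one change score, 3 if there are two (v2−v1 and v3−v1). This range is needed because v2 and v3 are undefined.
- Assumed for simulation: exponential PFS with median 8 months, uniform censoring at 5 to 17 months, between-protein correlation 0, 0.3 or 0.6.

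**1. The plan's own figure.** No error rate or power is given for the biomarker work. The only related figure is N. With ORR 43% against 65%, one-sided 0.05 and power 0.80:

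n = [1.645·√(0.43×0.57) + 0.842·√(0.65×0.35)]² / 0.22² = 30.54, rounded up to 31; 31/0.8 = 38.75, rounded up to 39.

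This reproduces the stated 39 and supplies the two sample sizes simulated below. It has no other bearing on this point.

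**2. Chance hits at unadjusted 0.05 if nothing is real.** Expected hits = 0.05·m. P(at least one) = 1 − 0.95^m if independent.

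| Log-rank tests, m | Expected false hits | P(at least one) |
|---|---|---|
| 92 | 4.6 | 0.991 |
| 184 | 9.2 | 0.9999 |
| 276 | 13.8 | >0.9999 |

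**3. Does correlation between proteins change this?** Null trials with n = 31 and n = 39 were simulated, 2,000 runs per setting. Across 276 tests the mean was 14.5 to 15.0 hits, and P(at least one) was 0.99 to 1.00 at every correlation. At correlation 0.6 the 95% range widens to about 2 to 56. For the 92 baseline tests alone, P(at least one) was 0.99, 0.97 to 0.98, and 0.86 at correlations 0, 0.3 and 0.6. Correlation makes the count less predictable but does not lower its mean.

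**4. With BH at 5% across all 276 tests.** In the same simulations, the chance of any false hit was about 5% to 8% and the mean number was 0.07 to 0.33.

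**5. Taxa.** The number of taxa is not given. If 50, 100 or 200 taxa were each tested at 0.05, the expected false hits per outcome would be 2.5, 5 or 10. This is arithmetic on an assumed taxon-level design.

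**6. Timing.** A protein unrelated to prognosis was given a common drift with time on treatment, and its change score was split at the median and tested against PFS (n = 39; 3,000 runs; Monte Carlo standard error near 5% is √(0.05×0.95/3000) = 0.4 percentage points). The progression column uses progressors only. The fixed sample is taken at 1.4 months (two 21-day cycles) in patients still progression-free.

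| Drift (SD/month, assumed) | Progression sample | Best-response sample | Fixed sample with landmark |
|---|---|---|---|
| 0 | 5.8% | 5.2% | 5.3% |
| 0.05 | 12% | 4.9% | 4.8% |
| 0.1 | 26% | 5.9% | 5.1% |
| 0.2 | 64% | 8.0% | 5.6% |

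Proteins that react to progression itself were not simulated.

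**The case against.** The strongest reply is that the plan already uses BH, mentions it twice, and labels the work exploratory. The second mention follows a sentence about two analyses that are not named, so BH may have been meant to cover more than the Cox models. A BH-adjusted p-value below 0.05 would also satisfy the blanket rule. This stands in part: the gap is undefined scope, not an instruction to ignore multiplicity. But an adjustment is named before the log-rank sentence and none after it, so an analyst following the text could properly report unadjusted log-rank p-values.

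A reader might infer four stronger things that the documents do not support:

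- *That unadjusted p-values are prescribed.* The text never says so. This is a reading of silence together with the 0.05 rule.
- *That every taxon will be tested at 0.05.* The rank and group tests are described for patient data and outcome parameters. For microbiota, section 3.2 mentions only diversity indices and unspecified statistical analysis. No taxon-level test is specified.
- *That the change scores produce false hits by construction.* With no drift the error rate is near nominal. Inflation needs drift, whose size is assumed here, and it is small for the best-response sample.
- *That false markers are almost sure to be named.* That holds only if nothing is real and log-rank p-values, not the BH-adjusted Cox results, decide what is reported.

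The link from v2 and v3 to best response and progression is likely but also inferred.

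**Conclusion.** The concern holds as a gap in the exploratory analysis plan that should be closed. No multiplicity adjustment is stated for the log-rank tests or across taxa. Under the global null, unadjusted log-rank testing would yield about 4.6 false hits for baseline alone and 9.2 to 13.8 once change scores are included. The expected counts do not depend on independence between proteins; the 99% chance of at least one baseline hit does.

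Testing a change score from a progression-timed sample against PFS from treatment start is unsound. Its size is conditional: about 6% false positives with no drift and 26% to 64% at assumed drifts of 0.1 to 0.2 SD per month. The best-response sample is little affected at those drifts (6% to 8%). This rests on reading v3 as the progression sample.

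The primary ORR conclusion, DCR, the Kaplan-Meier estimates of PFS and OS, and the sample size are untouched. The effect is on which biomarkers may be called significant.

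**What to change.** In the synopsis statistical analysis plan and in section 11:

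1. Base protein significance on the continuous Cox model per 1 NPX, with BH across all proteins and measures as one stated family. Show median-split Kaplan-Meier curves without significance claims, or apply BH to the log-rank p-values as well.
2. Apply BH across taxa within each outcome for any taxon-level tests, and say which tests these are.
3. Define v2 and v3.
4. Report changes at progression descriptively, with no PFS test.
5. For the on-treatment change score, count PFS from the sample date in patients still progression-free (landmark), or use a time-dependent covariate.

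Using the sample after cycle 2 for every patient is an option, since it is already collected. Section 6, however, runs the protein assay at the visit of best efficacy, so extra Olink assays may be needed for patients whose best response falls at another visit.

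Otherwise the cost is a few sentences and a few lines of code, with no change to treatment, endpoints or sample size. The downsides are fewer nominal hits and the loss of early progressors from the landmark analysis.
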